#### 11.2 Immune-related Response Criteria Derived from RECIST 1.1 (irRECIST)

Increasing clinical experience indicates that traditional response criteria may not be sufficient to fully characterize activity in this new era of targeted therapies and/or biologics.

This is particularly true for immunotherapeutic agents such as anti-CTLA-4 and anti-PD-1 / anti PD-L1 which exert the antitumor activity by augmenting activation and proliferation of T-cells, thus leading to tumor infiltration by T-cells and tumor regression rather than direct cytotoxic effects [31, 32]. Clinical observations of patients with advanced melanoma treated with ipilimumab, for example, suggested that conventional response assessment criteria such as Response Evaluation Criteria in Solid Tumors (RECIST) and WHO criteria are not sufficient to fully characterize patterns of tumor response to immunotherapy because tumors treated with

immunotherapeutic agentsmay show additional response patterns that are not described in these conventional criteria [33, 34].

Furthermore, the conventional tumor assessment criteria (RECIST and WHO criteria) have been reported as not capturing the existence of a subset of patients who have an OS similar to those who have experienced CR or PR but were flagged as PD by WHO criteria [34, 35].

On these grounds, a tumor assessment system has been developed that incorporates these delayed or flare-type responses into the RECIST 1.1 criteria (irRECIST) [33].

For irRECIST, only target and measurable lesions are taken into account. In contrast to the RECIST 1.1, the irRECIST criteria:

- require confirmation of both progression and response by imaging at least 4 weeks from the date first documented, and
- do not necessarily score the appearance of new lesions as progressive disease if the sum of lesion diameters of target lesions (minimum of 10 mm per lesion, maximum of 5 target lesions, maximum of 2 per organ) and measurable new lesions does not increase by >= 20%.

The same method of assessment and the same technique should be used to characterize each identified and reported target lesion(s) at baseline and throughout the trial.

irRECIST criteria are defined as follows:

- Overall immune-related complete response (irCR): Complete disappearance of all lesions (whether measurable or not) and no new lesions. All measurable lymph nodes also must have a reduction in short axis to <10 mm.
- Overall immune-related partial response (irPR): Sum of the diameters (longest for nonnodal lesions, shortest for nodal lesions) of target and new measurable lesions decreases >= 30%.
- Overall immune-related stable disease (irSD): Sum of the diameters (longest for nonnodal lesions, shortest for nodal lesions) of target and new measurable lesions neither irCR, irPR, (compared to baseline) or immune-related progressive disease (irPD, compared to nadir).
- Overall immune-related progressive disease (irPD): Sum of the diameters (longest for non-nodal lesions, shortest for nodal lesions) of target and new measurable lesions increases >= 20% (compared to nadir), confirmed by a repeat, consecutive observation at least 4weeks from the date first documented.

New measurable lesions: Incorporated into tumor burden (ie, added to the target lesion measurements). A lymph node has to be  $\geq 15$  mm in short axis to be a measurable new lesion and its short axis measurement is included in the sum. Up to 2 new lesions per organ and up to 5 new lesions in total can be added to the measurements.

New non-measurable lesions: Do not define progression but preclude irCR.

Overall responses derived from changes in index, non-index, and new lesions are outlines in the table.

Table 11: Overall Resp	onse for irRECIST Derived from	Changes in Index, Non-i	ndex and
New Lesions			

Measurable Response	Non-measurab	Overall Response using irRECIST b	
Index and New Measurable Lesions (Tumor Burden)a	Non-Index Lesions	New non- measurable lesions	
Decrease 100%	Absent	Absent	irCR
Decrease 100%	Stable	Any	irPR
Decrease 100%	Unequivocal progression	Any	irPR
Decrease $\geq 30\%$	Absent / stable	Any	irPR
Decrease $\geq 30\%$	Unequivocal progression	Any	irPR
Decrease < 30% and increase <20%	Absent/ stable	Any	irSD
Decrease < 30% and increase <20%	Unequivocal progression	Any	irSD
Increase ≥ 20%	Any	Any	irPD

a. Decrease assessed relative to baseline. Increase assessed relative to nadir.

b. Response (irCR and irPR) and progression (irPD) must be confirmed by a second, consecutive assessment at least 4 weeks apart.

#### 11.3 Methods for Evaluation of Disease

All measurements should be taken and recorded in metric notation using a ruler, calipers, or a digital measurement tool. All baseline evaluations should be performed as closely as possible to the beginning of treatment and never more than 4 weeks before the beginning of the treatment.

The same method of assessment and the same technique should be used to characterize each identified and reported lesion at baseline and during follow-up. Imaging-based evaluation is preferred to evaluation by clinical examination unless the lesion(s) being followed cannot be imaged but are assessable by clinical exam.

Clinical lesions. Clinical lesions will only be considered measurable when they are superficial (*e.g.*, skin nodules and palpable lymph nodes) and  $\geq 10$  mm in diameter as assessed using calipers (*e.g.*, skin nodules). In the case of skin lesions, documentation by color photography, including a ruler to estimate the size of the lesion, is recommended.

Chest x-ray. Lesions on chest x-ray are acceptable as measurable lesions when they are clearly defined and surrounded by aerated lung; however, CT is preferable.

Conventional CT and MRI. This guideline has defined measurability of lesions on CT scan based on the assumption that CT thickness is 5mm or less. If CT scans have slice thickness greater than

5 mm, the minimum size of a measurable lesion should be twice the slice thickness. MRI is also acceptable in certain situations (*e.g.* for body scans).

Use of MRI remains a complex issue. MRI has excellent contrast, spatial, and temporal resolution; however, there are many image acquisition variables involved in MRI, which greatly impact image quality, lesion conspicuity, and measurement. Furthermore, the availability of MRI is variable globally. As with CT, if an MRI is performed, the technical specifications of the scanning sequences used should be optimized for the evaluation of the type and site of disease. Furthermore, as with CT, the modality used at follow-up should be the same as was used at baseline and the lesions should be measured/assessed on the same pulse sequence. It is beyond the scope of the RECIST guidelines to prescribe specific MRI pulse sequence parameters for all scanners, body parts, and diseases. Ideally, the same type of scanner should be used and the image acquisition protocol should be followed as closely as possible to prior scans. Body scans should be performed with breath-hold scanning techniques, if possible.

FDG-PET. While FDG-PET response assessments need additional study, it is sometimes reasonable to incorporate the use of FDG-PET scanning to complement CT scanning in assessment of progression (particularly possible "new" disease). New lesions on the basis of FDG-PET imaging can be identified according to the following algorithm:

- (a) Negative FDG-PET at baseline, with a positive FDG-PET at follow-up is a sign of PD based on a new lesion.
- (b) No FDG-PET at baseline and a positive FDG-PET at follow-up: If the positive FDG-PET at follow-up corresponds to a new site of disease confirmed by CT, this is PD. If the positive FDG-PET at follow-up is not confirmed as a new site of disease on CT, additional follow-up CT scans are needed to determine if there is truly progression occurring at that site (if so, the date of PD will be the date of the initial abnormal FDG-PET scan). If the positive FDG-PET at follow-up corresponds to a pre-existing site of disease on CT that is not progressing on the basis of the anatomic images, this is not PD.
- (c) FDG-PET may be used to upgrade a response to a CR in a manner similar to a biopsy in cases where a residual radiographic abnormality is thought to represent fibrosis or scarring. The use of FDG-PET in this circumstance should be prospectively described in the protocol and supported by disease-specific medical literature for the indication. However, it must be acknowledged that both approaches may lead to false positive CR due to limitations of FDG-PET and biopsy resolution/sensitivity.

Note: A "positive" FDG-PET scan lesion means one which is FDG avid with an uptake greater than twice that of the surrounding tissue on the attenuation corrected image.

PET-CT. At present, the low dose or attenuation correction CT portion of a combined PET-CT is not always of optimal diagnostic CT quality for use with RECIST measurements. However, if the site can document that the CT performed as part of a PET-CT is of identical diagnostic quality to a diagnostic CT (with IV and oral contrast), then the CT portion of the PET-CT can be used for RECIST measurements and can be used interchangeably with conventional CT in accurately measuring cancer lesions over time. Note, however, that the PET portion of the CT introduces additional data which may bias an investigator if it is not routinely or serially performed.

Tumor markers. Tumor markers alone cannot be used to assess response. If markers are initially above the upper normal limit, they must normalize for a participant to be considered in complete clinical response.

#### DATA REPORTING / REGULATORY REQUIREMENTS

Adverse event lists, guidelines, and instructions for AE reporting can be found in Section 7 (Adverse Events: List and Reporting Requirements).

#### 12.1 Data Reporting

#### 12.1.1 Method

The Office of Data Quality (ODQ) will collect, manage, and perform quality checks on the data for this study.

12.1.2 Responsibility for Data Submission

Investigative sites within DF/HCC or DF/PCC are responsible for submitting data and/or data forms to the Office of Data Quality (ODQ) in accordance with DF/HCC policies.

#### 12.2 Data Safety Monitoring

The DF/HCC Data and Safety Monitoring Committee (DSMC) will review and monitor toxicity and accrual data from this study. The committee is composed of medical oncologists, research nurses, pharmacists and biostatisticians with direct experience in cancer clinical research. Information that raises any questions about participant safety will be addressed with the Overall PI and study team.

The DSMC will review each protocol up to four times a year with the frequency determined by the outcome of previous reviews. Information to be provided to the committee may include: up-to-date participant accrual; current dose level information; DLT information; all grade 2 or higher unexpected adverse events that have been reported; summary of all deaths occurring within 30 days of intervention for Phase I or II protocols; for gene therapy protocols, summary of all deaths while being treated and during active follow-up; any response information; audit results, and a summary provided by the study team. Other information (e.g. scans, laboratory values) will be provided upon request.

#### 12.2 Multi-Center Guidelines

This protocol will adhere to DF/HCC Policy MULTI-100 and the requirements of the DF/HCC Multi-Center Data and Safety Monitoring Plan. The specific responsibilities of the Sponsor-Investigator, Coordinating Center, and Participating Institutions and the procedures for auditing are presented in Appendix B.

#### STATISTICAL CONSIDERATIONS

This is an open label, two-stage, non-randomized phase 2 trial examining mirvetuximab soravtansine (IMGN853) and pembrolizumab in participants with advanced or recurrent serous endometrial cancer (EC). The combination will be tested in patients with microsatellite stable (MSS) and FR $\alpha$  positive tumors.

Enrollment will follow a standard Simon two-stage optimal design for a single cohort to inform whether the combination has significant clinical activity worthy of further evaluation. Statistical considerations are developed for a co-primary objectives to evaluate the objective response rate (ORR) and rate of progression-free survival at 6 months (PFS6), with a two-stage design that allows for early stopping for futility.

Target enrollment is a maximum of 35 patients. Up to 19 patients of the total cohort may have received prior therapy targeting the PD-1/PD-L1 pathway.

#### 13.1 Study Design/Endpoints

#### Primary Endpoints

To assess the activity of mirvetuximab soravtasine in combination with pembrolizumab in patients with recurrent or persistent MSS and FR $\alpha$  positive endometrial cancer by evaluating the frequency of patients who survive progression-free for at least 6 months (PFS6) after initiating therapy or have objective tumor response.

Statistical considerations are developed for co-primary objectives to evaluate the objective response rate (ORR) by RECIST 1.1 and rate of progression-free survival at 6 months (PFS6), with a two-stage design that allows for early stopping for futility.

A two-stage test was constructed using the method of Sill, Rubinstein, Litwin and Yothers [36] with the goal of stopping early for futility to limit patient exposure to an inactive agent while restricting the probabilities of type I and type II errors to approximately 10% and 15%, respectively. For the co-primary endpoints, a true ORR of 5% or less and a rate of progressionfree survival at 6 months of (PFS6) 10% or less would not be of clinical interest (H0:  $\pi_{OR} \leq 5\%$ AND  $\pi_{PFS6} \le 10\%$ ), whereas an improvement to a 20% objective response rate or 30% PFS6 rate would warrant further investigation of the study treatment. In the first stage, 16 patients will be enrolled and accrual will pause. If there are at least two objective responses or two patients progression-free at 6 months among the first 16 patients, the second stage of accrual will commence where an additional 19 patients will be enrolled. If at the end of the trial there are at least 4 treated patients with an objective response or 8 patients progression-free at 6 months, the study treatment will be considered worthy of further study. Specifically, analysis of historical data (GOG129 and GOG229 series) based on similar population of patients with endometrial cancer where the levels of activity were believed to be inactive to modestly active shows that an unacceptable rate for objective response ( $\pi_{OR}$ ) is 5% and for PFS6 ( $\pi_{PFS6}$ ) is 10%, respectively. A bivariate test of the co-primary endpoints is constructed as follows:

H0:  $\pi_{OR} \leq 5\%$  AND  $\pi_{PFS6} \leq 10\%$ 

vs. H1:  $\pi_{OR} > 5\%$  OR  $\pi_{PFS6} > 10\%$ 

Targeted alternative hypothesis: An absolute improvement in the rate of OR by 15% or PFS6 by 20% would be of clinical interest. Power is determined under two specific hypotheses (Hr:  $\pi_{OR} = 20\%$ ,  $\pi_{PFS6} = 10\%$ ) and (Hs:  $\pi_{OR} = 5\%$ ,  $\pi_{PFS6} = 30\%$ ) where sufficient activity is seen in only each endpoint, respectively. Sample size is selected to have sufficient power to reject the null under cases that assume either (a) independence or (b) dependence among the co-primary endpoints. The decision rules and operating characteristics of the two-stage design are summarized in the Table below:

	Endpoint	Objective	PFS6
		Response	
	Null hypothesis	5%	10%
	Alternative Hypothesis	20%	30%
Stage 1	Number of Patients	16	
	Minimum number of	2	2
	events to continue to		
	Stage 2		
	PET (Independence)	0.417	
	PET (Dependence)	0.502	
Stage 2	Number of Patients	35	
	Minimum number of	4	8
	events to reject the null		
	hypothesis		
	Alpha (Independence)	0.098	
	Alpha (Dependence)	0.88	
	Power (Independence)	0.889	0.873
	Power (Dependence)	0.846	0.862

 Table 12: Decision rules and operating characteristics of the two-stage design

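### Table 12 prints a type I error of 0.88 under dependence; the design's own rule gives 0.088

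*Combined protocol and SAP*

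**What the plan says.** Section 13.1 describes a two-stage test on two co-primary endpoints, objective response (OR) and PFS6, built with the goal of stopping early for futility while "restricting the probabilities of type I and type II errors to approximately 10% and 15%, respectively".

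- **Stage 1.** Accrual continues "If there are at least two objective responses or two patients progression-free at 6 months among the first 16 patients" and, if that is met, "an additional 19 patients will be enrolled", for 35 in total.
- **Final rule.** The treatment passes if there are "at least 4 treated patients with an objective response or 8 patients progression-free at 6 months".
- **Rates.** The null rates are 5% (OR) and 10% (PFS6). The targets are 20% and 30%, and power is taken at (20%, 10%) and at (5%, 30%).

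Table 12 then lists operating characteristics under independence and under dependence of the two endpoints. Under independence it gives an early-stopping probability under the null (PET) of 0.417, alpha 0.098, and power 0.889 and 0.873. Under dependence it gives PET 0.502, power 0.846 and 0.862, and "Alpha (Dependence) 0.88". The strength of the dependence is not stated. Sections 13.4 and 13.5 only refer back to Section 13.1.

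**The concern.** The 0.88 disagrees with the 10% target in the text, with the 0.098 printed just above it, and with the PET of 0.502 in the same table. Read literally, it says that an inactive regimen would be declared promising 88% of the time when the endpoints are correlated. Some positive correlation is to be expected, because response and six months without progression reflect the same tumour course in the same patient.

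The text gives target error rates, but Table 12 is the only place with a calculated type I error under dependence. A reader who suspects a slip cannot recover the right value directly from the page, because the dependence setting is missing. The wrong figure would pass into any report that copies the table.

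**Working it through.** **Inputs (Section 13.1 and Table 12).** n1 = 16, n2 = 19, n = 35. Continue if OR ≥ 2 or PFS6 ≥ 2 among 16. Reject the null if OR ≥ 4 or PFS6 ≥ 8 among 35. Null rates are 0.05 and 0.10. Power is evaluated at (0.20, 0.10) and (0.05, 0.30).

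**Model.** Each patient falls in one of four OR × PFS6 cells. Let p11 be the probability of having both outcomes. Then P(OR only) = pOR − p11, P(PFS6 only) = pPFS6 − p11, and the remainder have neither. The joint counts for 16 and then 19 patients are enumerated exactly:

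- PET = P(OR1 ≤ 1 and PFS6_1 ≤ 1)
- alpha = P(stage 1 continues, and OR ≥ 4 or PFS6 ≥ 8 among 35), evaluated at the null rates

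**Step 1: reproduce the independence figures (p11 = pOR × pPFS6).** PET can be checked by hand:

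- P(OR1 ≤ 1) = 0.95^16 + 16 × 0.05 × 0.95^15 = 0.4401 + 0.3706 = 0.8108 (from unrounded terms)
- P(PFS6_1 ≤ 1) = 0.90^16 + 16 × 0.10 × 0.90^15 = 0.1853 + 0.3294 = 0.5147
- PET = 0.8108 × 0.5147 = 0.4173

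| Independence | Table 12 | Recomputed |
|---|---|---|
| PET | 0.417 | 0.4173 |
| Alpha | 0.098 | 0.0977 |
| Power at (20%, 10%) | 0.889 | 0.8885 |
| Power at (5%, 30%) | 0.873 | 0.8728 |

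All four agree to three decimals, so the rule has been read as the authors meant it.

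**Step 2: rule out 0.88 without assuming any particular dependence.**

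- A trial stopped at stage 1 cannot reject the null, so alpha ≤ 1 − PET = 1 − 0.502 = 0.498.
- Rejection needs at least one endpoint to reach its final threshold, so alpha ≤ P(OR ≥ 4 of 35 at 5%) + P(PFS6 ≥ 8 of 35 at 10%) = 0.0958 + 0.0200 = 0.1157 (from unrounded terms).
- Under the null, p11 can lie anywhere from 0 to 0.05. Over that range exact alpha runs from 0.0984 (p11 = 0) down to 0.0864 (every responder also a PFS6 success).

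**Step 3: recover the intended value.** Two routes agree.

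- *Solve p11 from the printed PET.* PET = 0.502 needs p11 = 0.0451, which means about 90% of responders are also PFS6 successes. Alpha is then 0.0879. Allowing for rounding of the PET (0.5015 to 0.5025), alpha is 0.0880 to 0.0878.
- *Use one overlap setting throughout.* Take p11 = 0.9 × the smaller marginal rate:

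| Dependence | Table 12 | Recomputed |
|---|---|---|
| PET | 0.502 | 0.5016 |
| Alpha | **0.88** | **0.0880** |
| Power at (20%, 10%) | 0.846 | 0.8458 |
| Power at (5%, 30%) | 0.862 | 0.8618 |

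A simulation of 1,000,000 trials at p11 = 0.0445 gave PET 0.501 and alpha 0.088, in line with the enumeration.

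**The case against.** The arithmetic is not in dispute. Four points can be made about how much weight the error deserves.

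1. **The text already states the intended error rate, and the row above prints 0.098.** A careful reader would see a slip and would not believe the 88%. This stands, and it means the trial's error control is not in doubt. It does not supply the missing figure, because the text gives approximate targets only.
2. **Nothing in the design depends on this cell.** This also stands. The stage 1 and final rules are stated in both the text and the table, and they hold alpha between 0.086 and 0.098 whatever the dependence.
3. **The cell may have been misread when the PDF was converted to text.** This cannot be excluded. It is the only operating characteristic in Table 12 with two decimals, which fits either a source typo or a lost character. Every other one came through intact and reproduces, and nothing shows that this cell was misread. It is a reason to look at the source page.
4. **The 0.9 overlap is inferred.** True: the documents give no dependence parameter. The setting matches three printed values, but it should be put to the authors as a value consistent with their table, for them to confirm. The exclusion of 0.88 does not rest on it.

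**Conclusion.** The concern holds. The printed 0.88 is impossible and is ten times the value of 0.088 that the stated rule yields. The impossibility follows from the table's own PET and from a bound that holds under any dependence. The specific value 0.088 rests on one assumption, that the unstated dependence is the one implied by the printed PET of 0.502; the two dependence power figures support the same setting. Under any other feasible dependence the correct entry would still lie between 0.086 and 0.098.

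This is an error in a reported operating characteristic of the primary test and must be corrected. It is not a flaw in the design: the sample size, stopping rule and final rule stand, and the type I error meets the target of about 10%.

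**What to change.** 1. Check the cell against the source page of Table 12. If it reads 0.88 there, change Alpha (Dependence) to 0.088.
2. Add a note to Table 12 stating the dependence between OR and PFS6 used for the dependence rows, as confirmed by the study statistician. The printed figures are reproduced by P(both) = 0.9 × the smaller marginal rate. If a different setting was used, state it and recompute the four dependence entries from it.

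The cost is one number and one table note. Sample size, decision rules, conduct and analysis do not change.

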#### 13.2 Sample Size, Accrual Rate and Study Duration

#### **Table 13: Accrual Target Demographics**

Accrual Targets					
Ethnic Category	Sex/Gender				
	Females		Males		Total
Hispanic or Latino	5	+	0	=	5
Not Hispanic or Latino	30	+	0	=	35
Ethnic Category: Total of all subjects	35	+	0	=	35
Racial Category					
American Indian or Alaskan Native	0	+	0	=	0
Asian	5	+	0	=	5

NCI Protocol #: N/A DF/HCC Protocol #: 18-602 Protocol Version Date: December 11, 2023

Black or African American	3	+	0	=	3
Native Hawaiian or other Pacific Islander	0	+	0	=	0
White	27	+	0	=	27
Racial Category: Total of all subjects	35	+	0	=	35
	35		0	Ι	35

#### 13.3 Stratification Factors

N/A

13.4 Interim Monitoring Plan

See Section 13.1

